member of the study staff with venipuncture training or CTRC nursing personnel will collect approximately two teaspoons (10 mL) of venous blood by peripheral venipuncture and the participant will collect half a cup of urine (20 mL) via a clean-catch method for analysis. Participants will be provided with a handout describing the “low plant diet” (Section I.4.) that they are to follow prior to each study visit, should they qualify for the study. The visit is expected to take 45-60 minutes.

A study clinician will review screening and laboratory results prior to participant enrollment. Participants will be contacted by phone and told whether they qualify for the study or not. Participants meeting all final eligibility criteria will be invited to participate in the intervention phase of the study and will be scheduled for Study Visit 1. Any participants with abnormal health screening or laboratory evaluation will be directed to their primary care physician for treatment and excluded from the study. In the event that a participant does not qualify for the study, their data will be destroyed at the end of the study.

I.4. Study visits 1 and 2

Visit timing: Visit 1 will occur a minimum of 72 hours following the screening visit to ensure adequate time for the low plant diet (Section I.4.), the screening laboratory results and for scheduling of appropriate facilities. Visit 2 will occur approximately 2-4 weeks following Visit 1 to allow for complete wash out of the study intervention (Figure 3).

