Sample collection: Participants will be asked to fast for 10-12 hours beginning at 9:00 PM the day prior to each study visit, excluding water, in an attempt to standardize gastrointestinal transit time and minimize delayed absorption of the study intervention due to the presence of food. A study clinician or CTRC nursing staff member will place a peripheral intravenous catheter in the participant’s arm or hand to allow for serial plasma specimen collection. Prior to administration of the *Centella asiatica* product, a baseline plasma sample of one tablespoon (15 mL) will be collected through the catheter using a syringe and transferred immediately into a heparinized Vacutainer tube. The participant will be asked to consume by mouth one of the two doses of *Centella asiatica* product dissolved in 8-12 ounces of warm water, on an empty stomach in the presence of study personnel to ensure compliance. Participants will be asked not to consume food for two hours following consumption of the study intervention to allow for transition into the small intestine and absorption. If signs of hypoglycemia present, participants will be allowed to consume a high glycemic food and monitored for improvement. Serial blood samples (two

Study Title: A pharmacokinetic study of *Centella asiatica* in the elderly

Principal Investigator: [name]

IRB#: 17697

Date: Feb 28 2024

Protocol v4.0

teaspoons (10 mL)/sample) will be obtained through the peripheral intravenous catheter using a syringe over a 12-hour post-administration period (15, 30, 45, 60, 90, 120, 180, 240, 360, 480, 600, and 720 min) (Table 2). Participants will collect their urine for the duration of the study visit (12-hours) to assess for excretion of *Centella asiatica* metabolites.

Tolerability and safety: We will record weight, height, body mass index, age, blood pressure, temperature and pulse rate at each study visit to monitor for adverse events and asymptomatic illnesses that may impact study results (Figure 3, Table 2). Participants will have an electrocardiogram (EKG) at the beginning of each study visit and six hours after intervention administration. Participants will be interviewed and administered a standardized multi-system adverse events questionnaire at the beginning and end of each study visit. This questionnaire has been adapted from the National University of Natural Medicine approved questionnaire and has been included in this IRB submission for approval.

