I.5. Visit 1 and 2 tolerability phone assessment

Participants will be telephoned the day following each study visit to assess for delayed adverse events and/or complications from the intravenous catheter placement using interviews and a standardized multi-system adverse events questionnaire (Figure 3, Table 2). Participants will be instructed to contact a study clinician if they experience any reactions following the phone assessment, and prior to their second study visit or one-week exit interview.

I.6. Exit interview tolerability assessment

Participants will be telephoned one week following the completion of their second study visit, or first study visit if they elect to drop out of the study, to assess for delayed adverse events and/or complications from the intravenous catheter placement using interviews and a standardized multi-system adverse events questionnaire (Figure 3, Table 2).

Table 2. Schedule of study visits and assessments.

	Screening	Visit 1	Visit 1 + 1 day	Visit 2	Visit 2 + 1 day	Visit 2 + 7 days
Event		Study visit	Phone visit	Study visit	Phone visit	Phone visit
Informed consent	•					
Vitals+	•	•		•		
Health screening, biometric assessment	•	•		•		
Electrocardiogram (EKG)		•		•		
Blood draw (CBC, CMP*) and urinalysis	•					
Low plant diet (starting 48h prior to visit)		•		•		
Single dose of intervention		•		•		
Blood collected at intervals (0-12hr) for bioavailability and antioxidant assessment	•^	•		•		
12-hour urine collection, baseline urinalysis		•		•		
Adverse events (AE) questionnaire		•	•	•	•	•

Study Title: A pharmacokinetic study of *Centella asiatica* in the elderly

Principal Investigator: [name]

IRB#: 17697

Date: Feb 28 2024

Protocol v4.0

Vitals include blood pressure, temperature and pulse rate

* CBC = Complete Blood Count with differential; CMP = Comprehensive Metabolic Panel

[^] Single time point

I.7. Subject participation duration

Including the screening visit, a two to four-week interval between doses, and an exit phone interview for adverse event monitoring, it will take a participant six to eight weeks to complete the study.

J. STUDY DURATION

Recruitment and data collection is expected to begin upon approval from the IRB and FDA and continue for seven months. We estimate a total of four months for final data analysis. Total estimated study duration is eleven months (Table 3).

Table 3. Study timeline.

Activity	Month	1-3	4-6			7-9			10-12		
Finalize product manufacture/quality control											

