Each analyte of interest from *Centella asiatica* will be identified by its retention time and characteristic mass spectral fragmentation pattern using selected reaction monitoring (MS/MS). The peak area ratio to the appropriate internal standard will be identified and evaluated against the standard calibration curve of each analyte. Each analyte's concentration will be used to generate a concentration-time curve for pharmacokinetic profiling. Pharmacokinetic profiling will use non-compartmental analysis to calculate common pharmacokinetic parameters such as peak concentration (C_{max}), the time at peak concentration (t_{max}) and the total 12-hour bioavailability represented by the total area under the curve (AUC_{0-12}). These will be compared to our mouse data in order to assess appropriateness of dosing level. Other calculable non-compartmental analysis metrics will also be determined, such as the elimination half-life ($t_{1/2}$) calculated from the profile tails and the mean residency time of the compounds in plasma. Descriptive assessment will be done at each of the doses to give basic pharmacokinetic summarization of the various *Centella asiatica* compounds and total antioxidant compounds measured by ferric reducing ability of plasma. Dose dependence of the study outcomes will be determined by evaluation of the within-subject differences in study outcomes between the different doses. For all continuous variables, dose effects will be evaluated both naively using paired t-tests and with ordinary least-squares regression with correction for commonly cited confounders including but not limited to baseline age and gender. Assumptions of normality will be confirmed using outcome density distributions alongside utility from formal tests, such as the Anderson-Shapiro. In instances of normality violation, statistical transformation such as natural logs and square roots will be considered, as will non-parametric equivalent tests such as the paired Wilcoxon rank-sum test. Standard diagnostics will be very conservative given the limited number of available participants but the effect of removing clearly obvious outliers will be evaluated. Although all *Centella asiatica* compounds of interest and pharmacokinetic parameters are defined *a priori*, multiple comparison correction to p-values will be applied as necessary, with final two-tail significance defined at $p<0.05$.

L.2. Sample size

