completed at the screening visit in order to collect data on any/all pre-existing symptoms and their severity, and will serve as baseline data to determine attribution to the study intervention. The Adverse Event Monitoring Form will be administered in person at the beginning and end of Visits 1 and 2, via telephone the day following Visit 1 and 2, and by telephone one week after Visit 2, to assess for acute and delayed adverse events. Electrocardiograms will be performed just prior to administration of *Centella asiatica* product and six hours after intervention to monitor for adverse events.

Participants will be reminded and encouraged during clinic visits to contact a study clinician if a moderate or serious AE occurs. Participants will be given a telephone number they can call at any time to report potential adverse effects. All severe AEs will immediately be reported to the Independent Monitoring Committee (IMC) and the OHSU IRB by the study principal investigator. Severe AEs (SAEs) are defined as events that are life-threatening or result in hospitalization, permanent disability, cancer, death, or another significant outcome.

N.1. Attribution to intervention

At each administration, items identified on the Adverse Event Monitoring Form will be compared to baseline levels to determine if the symptom was pre-existing. If the symptom was pre-existing at the same or a previously greater severity, the symptom will *not* be considered attributable to the study intervention. If the symptom was pre-existing at lesser severity (or was not previously present), the symptom may be considered attributable to the study intervention. If the intervention is considered attributable, [name] and [name], in consultation with the Principal Investigator, will determine if an alternative clinical explanation exists for the adverse event. If an alternative explanation does not exist, the adverse event *will* be considered attributable to the study intervention. If an alternative explanation does exist, the adverse event *will not* be considered attributable to the study intervention.

N.2. Independent Monitoring Committee (IMC)

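### Scheduled adverse-event contacts differ by period: the second dose gets a one-week call, while the first dose in a continuing participant gets none between day 1 and Visit 2

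*Combined protocol and SAP*

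**What the plan says.** Section I.5 schedules a call after both doses: "Participants will be telephoned the day following each study visit to assess for delayed adverse events". Section I.6 adds the one-week call: "Participants will be telephoned one week following the completion of their second study visit, or first study visit if they elect to drop out". Section N describes the calls as "via telephone the day following Visit 1 and 2, and by telephone one week after Visit 2, to assess for acute and delayed adverse events". Section F.1 places the last contact one week after study completion. Table 2 has a column for seven days after Visit 2 and none for seven days after Visit 1.

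The same questionnaire is also given in person. Section I.4 has it "administered a standardized multi-system adverse events questionnaire at the beginning and end of each study visit", and Section N agrees: "The Adverse Event Monitoring Form will be administered in person at the beginning and end of Visits 1 and 2". On spacing, Section I.4 says: "Visit 2 will occur approximately 2-4 weeks following Visit 1". Between contacts the plan relies on participants: "Participants will be instructed to contact a study clinician if they experience any reactions following the phone assessment" (Section I.5). Section I.2 has a call three days before Visit 2, described as a consent check and a reminder. No adverse-event questions are mentioned for it.

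**The concern.** Acute tolerability is Aim 2 and a secondary endpoint (Section A.3). Section C.4.4 says there are no human safety data for concentrated water extracts at the doses used here. The plan evidently regards a structured check one week after a dose as worth making, since it makes one after the last dose a person takes, whichever that is. It omits the check after the first dose in people who carry on, and gives no reason.

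Section O.1 expects transient gastrointestinal effects. An episode on, say, day 4 after the first dose may be over and poorly remembered by Visit 2. No recall period is stated for the questionnaire. Table 2 marks the blood count and metabolic panel at screening only, so finding a delayed effect depends largely on symptom reports. The termination rule in Section H.4 and the monitoring committee's review in Section N.3 rest on the same reports.

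Section L.1 says: "Dose dependence of the study outcomes will be determined by evaluation of the within-subject differences in study outcomes between the different doses". If tolerability is read in that spirit, each person's two doses are being compared with different contact timing and different recall.

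**Working it through.** The plan gives no figure to reproduce here. The check sets the schedules side by side and then works out what they imply for each dose.

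**Structured contacts after each dose (Sections I.4 to I.6, N, Table 2)**

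| | After first dose, continuing | After first dose, dropout | After second dose |
|---|---|---|---|
| End of visit | yes | yes | yes |
| Day 1 call | yes | yes | yes |
| Day 7 call | no | yes | yes |
| Start of Visit 2 (about day 14 to 28) | yes | no | not applicable |

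**Exposures without a one-week check.** 8 participants × 2 doses = 16 planned exposures. With no dropout, the 8 first-dose exposures have no day-7 contact: 8/16 = 50%.

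**Window by dose.** Inputs: 8 participants (Section F.2.1), random order (Section H.1) and allocation aimed at equal numbers per order (Section F.1). Let *a* participants take 2 g first and *b* take 4 g first. Let W1 and W2 be the days to the last structured contact after the first and second dose. With everyone completing:

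- mean window for 2 g = (*a*·W1 + *b*·W2)/8
- mean window for 4 g = (*a*·W2 + *b*·W1)/8

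Counting phone calls only, W1 = 1 and W2 = 7:

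- 4:4 gives (4 + 28)/8 = 4.0 days for 2 g and (28 + 4)/8 = 4.0 days for 4 g; difference 0.
- 5:3 gives (5 + 21)/8 = 3.25 and (35 + 3)/8 = 4.75; difference 1.5 days.
- 6:2 gives (6 + 14)/8 = 2.5 and (42 + 2)/8 = 5.5; difference 3.0 days.

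One dropout after Visit 1 from the 2 g-first arm of a 4:4 split. That person gets the day-7 call after 2 g and never takes 4 g:

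- 2 g: (3×1 + 1×7 + 4×7)/8 = 38/8 = 4.75 days
- 4 g: (3×7 + 4×1)/7 = 25/7 = 3.57 days

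Counting the questionnaire at the start of Visit 2 as well, W1 = 14 to 28 and W2 = 7:

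- 4:4 gives (4×14 + 4×7)/8 = 10.5 days for each dose at a 14-day interval, and (4×28 + 4×7)/8 = 17.5 days for each dose at 28 days.
- 5:3 at 14 days gives (5×14 + 3×7)/8 = 11.375 for 2 g and (5×7 + 3×14)/8 = 9.625 for 4 g.

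At 5:3 the dose with the longer window switches according to whether the Visit 2 form is counted. The plan does not say which contacts define the post-dose period, so even the direction of any imbalance is undefined.

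**The case against.** Three stronger readings are tempting, and the documents support none of them.

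A reader might infer that active follow-up after the first dose stops after one day. It does not. The full questionnaire is repeated at the start of Visit 2, so total ascertainment after the first dose spans 14 to 28 days, longer than the 7 days after the second. A dropout gets the one-week call but loses the Visit 2 assessment, so continuing participants are followed for longer overall, only later and with longer recall.

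A reader might infer that delayed reactions to the first dose are not looked for before the second. They are: by the interview and questionnaire at the start of Visit 2, and by vital signs and an electrocardiogram before dosing. Participants are also told to report reactions in the interval, have a number to call at any time, and the investigators review adverse events weekly (Section N).

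A reader might infer that 2 g and 4 g, as groups, are compared over unequal windows. Order is random and balance is sought, so the asymmetry belongs to the period and not to the dose. At 4:4 the difference is zero. Expected dropout is 10% of eight, or 0.8 of a participant. The tests named in Section L.1 are for continuous variables, and no test of adverse-event incidence by dose is described, so no specified analysis is invalidated.

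All of this stands, and it limits the weight of the point. It does not close the gap on days 2 to 7, which the Visit 2 form covers only by recall. Nor does it supply a defined post-dose window for the tolerability summary.

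**Conclusion.** The point holds as a difference between periods and is of minor weight. Within each completer the two doses are observed on different contact schedules, and the first-dose exposures, half of those planned, have no structured one-week check. Between doses the expected imbalance is nil with equal sequences. On calls alone it is 1.5 days at 5:3, 3.0 days at 6:2, and about 1.2 days (4.75 − 3.57) after a single 2 g-first dropout from 4:4. Equal sequences are an aim and not a guarantee, and Section F.2.1 contemplates falling to six subjects.

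These figures measure days to the last scheduled contact, not the number of events missed. The documents give no rate of delayed events from which to estimate that. The conclusion assumes that the call three days before Visit 2 contains no adverse-event questions, as its description suggests. If it does contain them, there is one more contact before Visit 2, but still none at one week.

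**What to change.** In Sections F.1, I.5, I.6 and N and in Table 2, add the same structured questionnaire by phone seven days after Visit 1 for all participants, continuing or not. At the stated spacing this falls before Visit 2. In Section L, state that adverse events will be summarised by dose and by period over a common 7-day post-dose window, and list later events separately.

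The cost is at most eight short calls (one per participant, and fewer in net terms because dropouts already receive one), using the existing form and staff, plus the wording changes. If the call cannot be added, the by-dose summary should still name a common window. The only post-dose contacts shared by both doses would then be the end of the visit and day 1, and the report should say so.

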Pharmacokinetics of *Centella asiatica* in the Elderly

NCT03929250

STUDY PROTOCOL INCLUDING STATISTICAL ANALYSIS PLAN

Document Version Date: February 28, 2024

Study Title: A pharmacokinetic study of *Centella asiatica* in the elderly

Principal Investigator: [name]

IRB#: 17697

Date: Feb 28 2024

Protocol v4.0

Title: A pharmacokinetic study of *Centella asiatica* in the elderly

A. OBJECTIVES

A.1. Purpose

The purpose of this pilot study is to measure the oral bioavailability and pharmacokinetics of known bioactive compounds from a standardized *Centella asiatica* water extract product (CAP) in cognitively healthy elders. Compound levels will be measured in human plasma and urine over 12 hours after acute oral administration of two doses of the botanical extract product. The dose giving maximum plasma levels (C_{max}) closest to those observed in our mouse studies, as well as the rate of clearance ($t_{1/2}$) of the known compounds, will be identified. These data will be used to inform decisions on the dosage and dosing frequency for future phase 1 and phase 2 clinical trials.

A.2. Primary goal

To determine the oral bioavailability and pharmacokinetics of known compounds from two single administrations of a *Centella asiatica* product in non-demented elders.

A.3. Endpoints

- The primary endpoints for this study are the maximum concentration (C_{max}), the area under the curve (AUC), and the time of maximum concentration (t_{max}) of known compounds from *Centella asiatica* (triterpenes and caffeoylquinic acids and their metabolites) in human plasma.
- A secondary endpoint is the half-life ($t_{1/2}$) of the known bioactive compounds and their metabolites to help determine dosage intervals.
- Additional secondary endpoints include temporal changes in ferric reducing ability of plasma (FRAP) as an indicator of antioxidant potential over time, tolerability and detection of acute adverse events through monitoring by participant interviews, biometrics, vital signs and questionnaires.

B. SPECIFIC AIMS

Aim 1: To assess the bioavailability and rate of clearance of *Centella asiatica* derived compounds in cognitively healthy elders through a pharmacokinetic study.

- **Hypothesis:** We hypothesize that the triterpene and caffeoylquinic acid components from *Centella asiatica* will be bioavailable, and a dose giving similar plasma levels to those associated with cognitive effects in mice can be achieved.

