Power analysis and sample size estimation for the dose-dependent pharmacokinetics of *Centella asiatica* analytes were derived from the literature, specifically the plasma dose response analysis of the triterpene asiatic acid by Grimaldi et. al.⁴⁵ after single acute administration of 30 mg and 60 mg of a *Centella asiatica* triterpene fraction. In a repeated measures cohort of 12 males, they found significant differences ($p<0.05$) in asiatic acid's peak plasma concentration (C_{max}) (30 mg: $0.70 \mu\text{g/ml} \pm 0.38$; 60 mg: $1.36 \mu\text{g/ml} \pm 0.45$; $d=1.57$) and 24-hour total bioavailability (AUC_{0-24}) (30 mg: 4.16 ± 3.81 ; 60 mg: 9.39 ± 3.53 ; $d=1.42$) between the two doses. This paper was chosen as an analog for the current study since a proportionally equimolar dose response shift in the pharmacokinetic profile of asiatic acid can be expected of the proposed *Centella asiatica* product doses. Under that assumption, a significant within-group dose response at $\alpha=0.05$ with at least 80% power would be found for C_{max} with six participants and for AUC_{0-12} with seven participants. Even if the inclusion of additional compounds in the

Study Title: A pharmacokinetic study of *Centella asiatica* in the elderly

Principal Investigator: [name]

IRB#: 17697

Date: Feb 28 2024

Protocol v4.0

water extract reduces the dose effect anticipated in the current study, a significant difference in the pharmacokinetic outcomes would still be seen with eight participants. We therefore, propose a cohort of four men and four women, which will enable dose responses to be seen within each gender individually, and allow for evaluation of an attenuated response by pooling gender or provide protection against study dropout.

L.3. Data quality and management

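### Section L.1 tests the 2 g versus 4 g difference only against zero, so its result neither shows nor refutes dose-proportional exposure; the within-person 4 g:2 g ratio with its confidence interval should be reported as well

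*Combined protocol and SAP*

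**What the plan says.** Section L.1 (Specimen analysis) sets out the dose comparison: "Dose dependence of the study outcomes will be determined by evaluation of the within-subject differences in study outcomes between the different doses". The tools are paired t-tests and ordinary least-squares regression adjusted for covariates such as age and gender. Log or square-root transformation, or a paired Wilcoxon test, is considered only if normality fails. Significance is two-tailed at 0.05. L.1 also plans descriptive summaries at each dose and a comparison of the parameters with the mouse data. It names no ratio of exposures, dose-normalised parameter, confidence interval or reference value other than no difference.

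Section L.2 (Sample size) starts from the premise that "a proportionally equimolar dose response shift in the pharmacokinetic profile of asiatic acid can be expected of the proposed" product doses. It concludes that a significant dose response "with at least 80% power would be found for C_{max} with six participants and for AUC_{0-12} with seven participants". It adds that significance is still expected with eight participants if other compounds in the extract reduce the dose effect. It mentions evaluating an attenuated response by pooling the genders, without a method.

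Section A.1 says the study will identify the dose whose Cmax is closest to the mouse value, and states of the results: "These data will be used to inform decisions on the dosage and dosing frequency for future phase 1 and phase 2 clinical trials". Section H.1 gives the human equivalent of the mouse intake as 1.4 g/day, which is below both tested doses.

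**The concern.** The planned test asks whether exposure at 4 g differs from exposure at 2 g. Under the premise of L.2 it should differ, and by a factor of about 2. The open question is how the increase compares with the doubling of the dose, and a p-value against zero does not address it. L.2 itself expects significance both when the shift is proportional and when it is reduced, so a report of significant dose dependence would be compatible with either.

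What is at stake is the later use of the data. Predicting exposure at a dose that was not tested needs an estimate of how exposure scales between 2 g and 4 g, and of how uncertain that estimate is. The plan as written produces neither for Cmax or AUC0-12.

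**Working it through.** **Inputs from L.2** (published asiatic acid data, 30 mg versus 60 mg of a triterpene fraction):
- Cmax: 0.70 (SD 0.38) and 1.36 (SD 0.45) µg/ml, d = 1.57. Difference 0.66; ratio 1.36/0.70 = 1.94.
- AUC0-24: 4.16 (SD 3.81) and 9.39 (SD 3.53), d = 1.42. Difference 5.23; ratio 9.39/4.16 = 2.26.
- From L.1 and F.2.1: two-sided alpha 0.05; eight participants, or six after 25% dropout.

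**Step 1: the plan's own sample size.** Paired t-test power is P(|T| > t(0.975, n−1)), where T is noncentral t with n−1 degrees of freedom and noncentrality d√n.
- Cmax, d = 1.57: power 0.863 at n = 6.
- AUC, d = 1.42: power 0.792 at n = 6 and 0.876 at n = 7.

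The stated six and seven are reproduced. At n = 8 the power is 0.97 and 0.93.

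**Step 2: standard deviation of the within-person difference.** Reading d as mean difference divided by SD of differences gives 0.66/1.57 = 0.42 for Cmax and 5.23/1.42 = 3.68 for AUC. These correspond to a within-person correlation of about 0.50; for Cmax, (0.38² + 0.45² − 0.42²)/(2 × 0.38 × 0.45) ≈ 0.50. The documents do not say how d was obtained. Pooled-SD values would be 1.58 and 1.42, so the correlation is implied, not reported.

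**Step 3: the planned test by true ratio R, n = 8.** Here d(R) = low-dose mean × (R − 1)/SD of differences. At R = 1.5, Cmax gives 0.70 × 0.5/0.42 = 0.83 and AUC gives 4.16 × 0.5/3.68 = 0.56.

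| True 4 g:2 g ratio | Power, Cmax | Power, AUC |
|---|---|---|
| 1.4 | 0.37 | 0.20 |
| 1.5 | 0.53 | 0.28 |
| 1.75 | 0.86 | 0.54 |
| 2.0 | 0.98 | 0.78 |

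This holds the SD of differences fixed and lets the 24-hour AUC stand in for AUC0-12, as L.2 does. Cmax is often significant when the increase is well short of doubling. AUC misses significance in about 1 − 0.78 = 22% of studies even when exposure exactly doubles.

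**Step 4: the observed ratio at which p reaches 0.05.** The critical difference is 2.365 × SD/√8. For Cmax it is 2.365 × 0.42/√8 = 0.35, a ratio of 1 + 0.35/0.70 = 1.50. For AUC it is 2.365 × 3.68/√8 = 3.08, a ratio of 1 + 3.08/4.16 = 1.74.

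**Step 5: what a ratio with its interval would give.** On the log scale, SD of the log-ratio = √(2 ln(1 + CV²)), and the 95% interval multiplies or divides the ratio by exp(t × SD/√n). The documents give no within-person CV. Dividing SD of differences/√2 by the average of the two dose means gives 0.297/1.03 = 29% for Cmax and 2.60/6.78 = 38% for AUC. These are assumptions that rest on the implied correlation.
- CV 29%, n = 8: SD 0.402; 2.365 × 0.402/√8 = 0.336; factor 1.40. Around an observed ratio of 2: 1.4 to 2.8.
- CV 38%, n = 8: SD 0.519; 2.365 × 0.519/√8 = 0.434; factor 1.54. Around 2: 1.3 to 3.1.
- Range, n = 8: CV 20% has factor 1.26 (1.6 to 2.5); CV 50% has factor 1.75 (1.1 to 3.5).
- n = 6: 2.571 × 0.402/√6 = 0.422 gives 1.3 to 3.0 at 29%; 2.571 × 0.519/√6 = 0.545 gives 1.2 to 3.4 at 38%.

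**The case against.** The strongest reply is that proportionality is not what this pilot set out to measure. It appears in no objective, endpoint, aim or hypothesis. The rule in A.1, to find the tested dose whose Cmax lies nearest the mouse value, needs only exposure at each dose, and L.1 provides that through the summaries and the mouse comparison. No section commits to interpolating or extrapolating. This stands: a reader might infer that dose setting as planned depends on proportionality, and the documents do not say so. What remains is that A.1 also sends the data forward to dosage decisions in later trials, and that the mouse-equivalent intake in H.1 lies outside the tested range.

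A reader might also infer that significance is a foregone conclusion, or that the test answers alike at 1.4-fold and 2-fold. The plan's own figures contradict both: at a ratio of 1.4, power is 0.37 for Cmax and 0.20 for AUC. A starker picture arises only with an assumed CV of 20% on the log scale, where a 1.4-fold rise is significant 83% of the time and the 95% interval excludes 2 in 87%. At 29% these fall to 53% and 58%, and at 38% to 35% and 39%. The ratio analysis will therefore often be inconclusive too.

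Finally, the ratio can be formed from data the study already collects, and a log-scale paired analysis is allowed if normality fails. That shows the addition is cheap. It does not make it part of the plan.

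**Conclusion.** The point holds in a limited form and is worth acting on. The only planned inference on dose is against zero difference. Neither outcome of that test identifies proportional exposure: power is 0.53 and 0.28 (Cmax, AUC) at a true ratio of 1.5, and 0.98 and 0.78 at 2. These figures rest on the L.2 standard deviations carrying over to this product and population, and on reading the quoted d as a paired effect size.

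This is a gap in what will be estimated. The sample size is not wrong for its stated purpose. Nor could the study demonstrate saturation, as a reader might infer: two doses can suggest a ratio below 2, but they show neither the shape of the relation nor its cause. Carry-through of analyte already in pre-dose plasma, a possibility that K.3 allows for, would also lower the ratio. If true exposures are x and 2x and a baseline b is left in, the observed ratio is (2x + b)/(x + b), which is below 2 for any b above zero.

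**What to change.** In L.1, for Cmax and AUC0-12 of each analyte, specify analysis on the log scale and report the within-person 4 g:2 g geometric mean ratio with its confidence interval, read against the nominal ratio of 2. If analyte content per sachet is quantified, use the assayed content ratio instead. H.1 mentions fingerprinting, quality control and stability work but does not state such an assay, so 2 should be the default. State that baseline-corrected concentrations are used where pre-dose plasma contains the analyte. Keep the test against no difference beside the ratio. Say explicitly that this is estimation, and neither a powered proportionality test nor evidence of saturation.

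The cost is a few sentences in the analysis plan and minor extra analysis on the same data, with no added participants or samples. The drawback is that the intervals will be wide, and wider still if only six participants complete.
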